8.1.1 Permanent Discontinuation from Study Treatment

Subjects may discontinue treatment for any of the reasons noted above, or for other reasons such as the development of a serious adverse event. To better communicate patient flow throughout the study, different study period situations are provided below:

- Subjects who discontinue the investigational product in Period 1 or Period 2 may continue in the study according to the visit schedule (Section 2).
- At Week 52/Visit 18, subjects who have previously discontinued the investigational product will continue to Visit 801 of the Follow-up Period.
- Subjects who discontinue the investigational product in Period 3 may continue in Period 3 and then proceed to Week 104/Visit 801 of the Follow-up Period.

Investigational product is to be discontinued for patients who experience clinically significant systemic hypersensitivity events (such as anaphylaxis) following administration of investigational product.

Appendix 1 Abbreviations and Definitions

NSAIDs

nonsteroidal anti-inflammatory drugs

Appendix 2 Clinical Laboratory Tests

Other Tests:

Treg/Th17	Biopsy material
QuantiFERON-TB Gold ^b or PPD	LY3074828 concentration (PK)
high sensitivity C-reactive protein (hsCRP)	CCI
Pregnancy ^c	Fecal calprotectin (FCP)
CCI	Exploratory storage samples (whole blood, serum, plasma, colonic tissue, stool, RNA and DNA)
Human immunodeficiency virus antibody ^d	Anti-LY3074828 antibodies (immunogenicity)
Hepatitis B surface antigen ^d	Clostridium difficile (C diff) ^d
Hepatitis B surface antibody ^d	Hepatitis C antibody ^d
Hepatitis B core antibody ^d	Hepatitis C RNA PCR (if indicated)
Hepatitis B DNA PCR (if indicated) ^e	Hypersensitivity Markers^f

Abbreviations: PCR = polymerase chain reaction; PK = pharmacokinetics; PPD = purified protein derivative;

Treg/Th17 = T-regulatory/T-helper 17 cells.

^f See Section 7.8.2.2.

Appendix 6 Additional Information on Systemic Drug Administration Reactions

Per investigator's judgement, in the absence of other plausible and more likely etiology, a systemic drug administration reaction is defined as the presence of any of the following symptoms (list is not exhaustive):

- Generalized urticaria or pruritus
- Angioedema at a location other than the injection site
- Throat tightness
- Difficulty swallowing/talking
- Stridor
- Chest tightness/dyspnea
- Wheeze/bronchospasm
- Hypoxemia
- Sense of impending doom
- Hypotension (systolic blood pressure change >20 mmHg from baseline)
- Syncope
- Cardiovascular collapse
- Vomiting
- Abdominal pain
- Diarrhea
- Bladder/bowel incontinence

LY+FUP	All LY3074828 (Lilly study drug) data for Periods 1-3 plus all Follow-Up combined
mBOCF	modified baseline observation carried forward
CCI	
MedDRA	Medical Dictionary for Regulatory Activities
CCI	
MMRM	mixed model for repeated measures
NAb	neutralizing antibody
Nab+	NAb positive

CCI	
NRI	non-responder imputation
NRS	numeric rating scale
OI	opportunistic infection
PD	pharmacodynamics
PGRC	Patient's Global Rating of Change
PGRS	Patient's Global Rating of Severity
PK	pharmacokinetics
PT	preferred term
PRO	patient-reported outcomes: a 2-item index comprised of the SF and AP items from the CDAI (unweighted)
PRO2	patient-reported outcomes-2: a 2-item index comprised of the SF and AP items from the CDAI (weighted)
Q4W	every 4 weeks
QIDS-SR16	Quick Inventory of Depressive Symptomatology–Self Report (16 Items)
REML	restricted maximum likelihood
RHI	Robarts Histopathology Index
SAE	serious adverse event
SAP	statistical analysis plan
SC	subcutaneous
SD	standard deviation
SES-CD	Simple Endoscopic Score for Crohn's Disease
SF	stool frequency
SF-36	36-Item Short Form Health Survey
SI	International System of Units
SMQ	standardized MedDRA query
SOC	system organ class
TE ADA-	treatment-emergent ADA negative

TE ADA+	treatment-emergent ADA positive
TEAE	treatment-emergent adverse event
ULN	upper limit of normal
US	United States

3. Revision History

SAP Version 1 was approved prior to the first permanent data transfer.

SAP Version 2 was approved prior to first unblinding. The overall changes and rationale for the changes incorporated in Version 2 are as follows:

- Reflected protocol amendment (a).
- Further defined subject populations, study periods, and baseline/postbaseline for analyses.
- Added exploratory endpoints not specified in protocol based on data from new publications.

4. Study Objectives

Table AMAG.4.1 shows the objectives and endpoints of the study as noted in the protocol. Further details on the endpoints, including derivations, are described in the corresponding section of this SAP.

Table AMAG.4.1. Objectives and Endpoints

Objectives	Endpoints
Primary	
To test the hypothesis that treatment with LY3074828 is superior to placebo in the proportion of subjects with endoscopic response at Week 12 , defined as 50% reduction from baseline in SES-CD	Proportion of subjects achieving endoscopic response at Week 12
Secondary	
To evaluate the safety and tolerability of treatment with LY3074828	AEs and discontinuation rates; mean change vital signs; laboratory values
To evaluate the effect of LY3074828 on the proportion of subjects with endoscopic response at Week 52 , defined as 50% reduction from baseline in SES-CD	Proportion of subjects achieving endoscopic response at Week 52
To evaluate the efficacy of treatment with LY3074828 as superior to placebo in endoscopic remission (defined as an SES-CD of <4 ileal-colonic or <2 for isolated ileal disease, and no subscore >1) at Week 12	Proportion of subjects achieving endoscopic remission at Week 12
To evaluate the effect of LY3074828 on the proportion of subjects with endoscopic remission (defined as an SES-CD of <4 ileal-colonic or <2 for isolated ileal disease, and no subscore >1) at Week 52	Proportion of subjects achieving endoscopic remission at Week 52
To evaluate the efficacy of treatment with LY3074828 as superior to placebo in PRO remission (defined as SF \leq 2.5 and AP \leq 1) at Week 12	Proportion of subjects achieving PRO remission at Week 12
To evaluate the effect of LY3074828 on the proportion of subjects with PRO remission (defined as SF \leq 2.5 and AP \leq 1) at Week 52	Proportion of subjects achieving PRO remission at Week 52
To evaluate the effect of LY3074828 on health outcomes/quality-of-life measures (including PGRS score, PGRC score, IBDQ score, SF-36 score, and FACIT-Fatigue) at Weeks 12 and 52	The mean change from baseline for PGRS score, IBDQ score, FACIT-Fatigue, and SF-36, and the mean PGRC at Weeks 12 and 52
To characterize the PK of LY3074828	Clearance and volume of distribution
Tertiary/Exploratory	
To evaluate the efficacy of treatment with LY3074828 as superior to placebo in PRO2 response (defined as a PRO2 reduction of \geq 5 points) at Week 12	Proportion of subjects achieving PRO2 response at Week 12
To evaluate the effect of LY3074828 on the proportion of subjects with PRO2 response (defined as a PRO2 reduction of \geq 5 points) at Week 52	Proportion of subjects achieving PRO2 response at Week 52

Objectives and Endpoints

Objectives	Endpoints
To evaluate the efficacy of treatment with LY3074828 as superior to placebo in PRO2 remission (defined as a PRO2 <8) at Week 12	Proportion of subjects achieving PRO2 remission at Week 12
To evaluate the effect of LY3074828 on the proportion of subjects with PRO2 remission (defined as a PRO2 <8) at Week 52	Proportion of subjects achieving PRO2 remission at Week 52
To evaluate the effect of LY3074828 on durability of endoscopic response at Week 52	Proportion of subjects achieving endoscopic response at Week 52 who also had endoscopic response at Week 12
To evaluate the effect of LY3074828 on durability of endoscopic remission at Week 52	Proportion of subjects achieving endoscopic remission at Week 52 who also had endoscopic remission at Week 12
To evaluate the effect of LY3074828 on durability of PRO2 response at Week 52	Proportion of subjects achieving PRO2 response at Week 52 who also had PRO2 response at Week 12
To evaluate the effect of LY3074828 on durability of PRO2 remission at Week 52	Proportion of subjects achieving PRO2 remission at Week 52 who also had PRO2 remission at Week 12
To evaluate the efficacy of treatment with LY3074828 as superior to placebo in the composite of endoscopic and PRO remission at Week 12	Proportion of subjects achieving both endoscopic and PRO remission at Week 12
To evaluate the effect of LY3074828 on the proportion of subjects with composite endoscopic and PRO remission at Week 52	Proportion of subjects achieving both endoscopic and PRO remission at Week 52
To evaluate the effect of LY3074828 on durability of composite endoscopic and PRO remission at Week 52	Proportion of subjects achieving both endoscopic and PRO remission at Week 52 who also had both endoscopic and PRO remission at Week 12
	
To evaluate the effect of LY3074828 on BMC reported using the BMC scale	Change from baseline in reported BMC, at all time points evaluated

Objectives and Endpoints

Objectives	Endpoints
To evaluate the effect of LY3074828 on QIDS-SR16 at Weeks 12 and 52	Change from baseline in reported QIDS-SR16 score at Weeks 12 and 52
To explore the development of any anti-LY3074828 antibodies that are formed and their effect on safety, PK, and PD of LY3074828	Proportion of subjects who are ADA+. Proportion of ADA+ subjects who experience certain immunogenicity-specific AEs. CCI [REDACTED]
To evaluate changes in CDAI from baseline	Changes from baseline in CDAI.
To assess the psychometric properties (including reliability, validity, and responsiveness) of the CCI [REDACTED], BMC, CCI [REDACTED].	CCI
To evaluate the elimination of neutrophils from the mucosa by histopathology at Week 52.	Absence of lamina propria and epithelial neutrophils at Week 52 assessed by 
 GHAS RHI
Exploratory (not in protocol)	
To evaluate the efficacy of treatment with LY3074828 as superior to placebo in PRO response (defined as 30% reduction from baseline in AP or SF with neither worse than baseline) at Week 12	Proportion of subjects achieving PRO response at Week 12.
To evaluate the efficacy of treatment with LY3074828 as superior to placebo in PRO response (defined as 30% reduction from baseline in AP or SF with neither worse than baseline) at Week 52	Proportion of subjects achieving PRO response at Week 52.
To evaluate the effect of LY3074828 on durability of PRO response at Week 52	Proportion of subjects achieving PRO response at Week 52 who also had PRO response at Week 12.
To evaluate the effect of LY3074828 on durability of PRO remission at Week 52	Proportion of subjects achieving PRO remission at Week 52 who also had PRO remission at Week 12.
To evaluate the effect of LY3074828 on PRO remission at Week 52 among PRO responders at Week 12	Proportion of subjects achieving PRO remission at Week 52 out of those patients who had PRO response at Week 12.
To evaluate the efficacy of treatment with LY3074828 as superior to placebo in the composite of endoscopic response and PRO remission at Week 12	Proportion of subjects achieving both endoscopic response and PRO remission at Week 12
To evaluate the effect of LY3074828 on the proportion of subjects with the composite of endoscopic response and PRO remission at Week 52	Proportion of subjects achieving both endoscopic and PRO remission at Week 52

Objectives and Endpoints

Objectives	Endpoints
To evaluate the effect of LY3074828 on durability of the composite endoscopic response and PRO remission at Week 52	Proportion of subjects achieving both endoscopic response and PRO remission at Week 52 out of the patients with endoscopic response and PRO remission at Week 12
To evaluate the efficacy of treatment with LY3074828 as superior to placebo in PRO1 remission (defined as SF \leq 1.5 and AP \leq 1 and no worse than baseline) at Week 12	Proportion of subjects achieving PRO1 remission at Week 12.
To evaluate the effect of LY3074828 on the proportion of subjects with PRO1 remission at Week 52	Proportion of subjects achieving PRO1 remission at Week 52.
To evaluate the effect of LY3074828 on CDAI Remission (defined as CDAI <150)	Proportion of subjects achieving CDAI Remission at Weeks 12 and 52.
To evaluate the effect of LY3074828 on CDAI Response (defined as a decrease in CDAI of at least 100 points or CDAI <150)	Proportion of subjects achieving CDAI Response at Weeks 12 and 52.
To evaluate the effect of LY3074828 on CDAI remission at Week 52 among CDAI Responders at Week 12	Proportion of subjects achieving CDAI Remission at Week 52 out of those subjects who achieved CDAI response at Week 12.

Abbreviations: ADA+ = positive for anti-drug antibodies; AE = adverse event; AP = abdominal pain; BMC = bowel movement count; CDAI = Crohn's Disease Activity Index; **CCI**; CRP = C-reactive protein; EC50 = half maximal effective concentration; Emax = maximum effect; FACIT-Fatigue = Functional Assessment of Chronic Illness Therapy–Fatigue; FCP = fecal calprotectin; GHAS = Global Histologic Disease Activity Score; IBDQ = Inflammatory Bowel Disease Questionnaire; NRS = numeric rating scale; PD = pharmacodynamics; PGRC = Patient's Global Rating of Change; PGRS = Patient's Global Rating of Severity; PK = pharmacokinetics; PRO = patient-reported outcomes; QIDS-SR16 = Quick Inventory of Depressive Symptomatology–Self Report (16 Items); RHI = Robarts Histologic Index; SES-CD = Simple Endoscopic Score for Crohn's Disease; SF = stool frequency; SF-36 = 36-Item Short Form Health Survey.

5. Study Design

Study AMAG is a multicenter, randomized, parallel-arm, placebo-controlled trial in which approximately 180 subjects will be randomized. Subjects will be stratified to the following categories, and the exact number enrolled in either group will be dependent upon the enrollment rate of each subject population:

- A minimum of approximately 30% of subjects will be naive to biologic Crohn's disease (CD) therapy (including experimental biologic CD therapy).
- At least 50% of the subjects will be prior biologic CD therapy-experienced (including experience with experimental biologic CD therapy).

[figure not shown]
Study Periods:

- Screening (approximately 4 weeks): Subjects will be evaluated for study eligibility ≤ 28 days before the baseline visit.
Period 1 (Weeks 0 to 12): A 12-week dosing period is designed to evaluate the efficacy and safety of LY3074828 administered intravenously at Weeks 0, 4, and 8. At baseline, subjects will be randomized with a 2:1:1:2 allocation across the 4 treatment arms (1000, 600, and 200 mg LY3074828, and placebo) and stratified on the basis of previous exposure to biologic therapy for treatment of CD.
- Period 2 (Weeks 12 to 52): Subjects will receive both IV and SC dosing to maintain blinding from Weeks 12 through 48.
 - All subjects who received LY3074828 treatment in Period 1 and who achieved an improvement in their Simple Endoscopic Score for Crohn's Disease (SES-CD) score from baseline at Week 12 (determined by the central reader) will be re-randomized evenly to either:
 - 1) continue Period 1 treatment assignment (IV LY3074828 1000 mg, 600 mg, or 200 mg every 4 weeks [Q4W]) with placebo administered subcutaneously.
 - 2) IV placebo Q4W with SC LY3074828 300 mg Q4W.
 - All subjects who received LY3074828 treatment in Period 1 and who did not achieve an improvement from baseline SES-CD score at Week 12 will receive IV LY3074828 1000 mg and SC placebo Q4W.
 - All subjects who received placebo in Period 1 will receive IV LY3074828 1000 mg and SC placebo Q4W.

Re-randomization will be stratified based on endoscopic response (i.e., achieving a 50% reduction in SES-CD score from baseline).

- Period 3 (Weeks 52 to 104): All subjects with clinical benefit and continuing on study treatment may proceed to Period 3 and receive SC 300 mg LY3074828 Q4W open label starting at Week 52 through Week 104. Clinical benefit is defined as having an endoscopic response (50% reduction from baseline in SES CD score), or a 25% reduction from baseline in SES CD score, combined with a 40% reduction from baseline in stool frequency (SF) or abdominal pain (AP) score. Subjects not receiving clinical benefit at Week 52 will discontinue treatment and will enter the Follow-Up period.

- Follow-Up Period (Weeks 104 to 120): At Week 104, subjects will stop treatment and be followed for safety for an additional 16 weeks. [Figure AMAG.5.1](#) illustrates the study design.

Abbreviations: ETV = early termination visit; IV = intravenous; Q4W = every 4 weeks; SC = subcutaneous; SES-CD = Simple Endoscopic Score for Crohn’s Disease.
 *Subjects who have not had any improvement in SES-CD score from baseline at Week 12, as determined by the central reader, will receive IV LY3074828 1000 mg + SC placebo.

NOTE:

Period 1:

- Subjects who discontinue treatment may continue in the study according to the visit schedule into Period 2.
- In IWRS these subject will be randomized as “No treatment for Period 2.”.
- Subjects who ETV will continue to Visit 804/ET.

Period 2:

- Subjects who discontinue treatment may continue in the study according to the visit schedule during Period 2.
- At Week 52/Visit 18, subjects who have previously discontinued treatment or do not have clinical benefit will continue to Visit 801 of the Follow-up Period.
- Subjects who ETV will continue to Visit 804/ET.

Period 3:

- Subjects who discontinue treatment in Period 3 may continue in Period 3 and then proceed to Week 104/Visit 801 of the Follow-up Period.

Figure AMAG.5.1. Study design.

6. A Priori Statistical Methods

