6.1. Inclusion Criteria

Subjects will be eligible for the study only if they meet all of the following criteria within the screening period, which is ≤ 28 days prior to the start of study treatment, unless specifically defined:

Type of Subject and Disease Characteristics

- [1] have had a diagnosis of Crohn's disease for ≥ 3 months before baseline
- [2] have active Crohn's disease as defined absolute SF ≥ 4 (loose and watery stools defined as Bristol Stool Scale Category 6 or 7) AND/OR AP ≥ 2 at baseline (refer Section 9.1.2 for details)
- [3] have a SES-CD score ≥ 7 (centrally read) for subjects with ileal-colonic or ≥ 4 for subjects with isolated ileal disease within 14 days before the first dose of study treatment

Prior IBD Treatment

- [4] must have received prior treatment for Crohn's disease (according to either "a)" or "b)" below or combination of both):
 - a) history of inadequate response to, or failure to tolerate treatment with aminosalicylates, 6-mercaptopurine (6-MP) or azathioprine (AZA), oral or IV corticosteroids or history of corticosteroid dependence (an inability to successfully taper corticosteroids without return of Crohn's disease)OR
 - b) have received treatment with ≥ 1 biologic agents (such as TNF antagonists, vedolizumab, experimental biologic Crohn's disease therapeutics) with or without documented history of failure to respond to or tolerate such treatment:
 - o The treatment must have been discontinued according to the following timeline:
 - anti-TNF therapy at least 8 weeks before baseline
 - vedolizumab treatment at least 12 weeks before baseline
 - experimental biologic Crohn's disease therapy at least 8 weeks before baseline.
- [5] may be receiving a therapeutic dosage of the following drugs:

- Oral 5-aminosalicylic (ASA) compounds: if the prescribed dose has been stable for at least 3 weeks before screening colonoscopy or stopped treatment at least 3 weeks prior to screening colonoscopy.
- Oral corticosteroids must be at a prednisone-equivalent dose of ≤ 20 mg/day, or ≤ 9 mg/day of budesonide, and have been at a stable dose for at least 3 weeks prior to the screening colonoscopy. If stopping oral corticosteroid treatment prior to baseline, they must be stopped at least 3 weeks prior to screening colonoscopy.

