9.1.5. Other Assessments

Crohn's Disease Activity Index (CDAI): CDAI is an 8-item disease activity measure comprised of 3 patient-reported and 5 physician-reported/laboratory items. Subject responses are summed over a 7-day period and subsequently weighted, yielding a total score range of 0 to 600 points with a score of <150 points defined as remission. A score of 220 to 450 points indicates moderate to severe disease activity, and a score of >450 points indicates severe disease activity.

Patient Reported Outcome 2 (PRO2) is a 2-item index comprised of the SF and AP items from the CDAI. The total PRO2 comprises the average daily scores over 7 days and is weighted using the CDAI multiplication factors for SF and AP items.

For both of these items (**CDAI and PRO2**), 7 days of subject-reported data within a 12-day period prior to a visit will be utilized to calculate scores. Data will be excluded from score calculation when collected on day(s) of colonoscopy prep, day of colonoscopy procedure, and 2 days after colonoscopy procedure.

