		CDAI Remission	See CDAI Total Score calculations above. Proportion of subjects with CDAI Total Score <150 at Week x. Endpoints: 
 • Proportion of subjects with CDAI remission at Week 12 • Proportion of subjects with CDAI remission at Week 52
		CDAI Response	See CDAI Total Score calculations above. Proportion of subjects achieving a CDAI reduction of ≥ 100 from baseline or CDAI <150 at Week x. Endpoints: 
 • Proportion of subjects with CDAI response at Week 12 • Proportion of subjects with CDAI response at Week 52
		CDAI Remission in CDAI Responders	Endpoints: 
 • Among CDAI responders at Week 12, the proportion of subjects with CDAI remission at Week 52.
Composite Endoscopic and PRO Remissions	Endoscopic remission: See SES-CD section above. PRO remission: See CDAI section above.	Composite of Endoscopic and PRO Remissions	Proportion of subjects achieving both endoscopic and PRO remissions at Week x. Endpoints : 
 • Proportion of subjects achieving both endoscopic and PRO remissions at Week 12 • Proportion of subjects achieving both endoscopic and PRO remissions at Week 52
		Durability of Composite Endoscopic and PRO Remissions	Endpoint : Proportion of subjects achieving both endoscopic and PRO remissions at Week 52 who also had both endoscopic and PRO remissions at Week 12 (that is, of those subjects who achieved both endoscopic and PRO remissions at Week 12, the proportion who maintained both endoscopic and PRO remissions at Week 52).

Description and Derivation of Efficacy Endpoints

Measure	Description / Timing	Variable	Derivation / Comment
Composite Endoscopic Response and PRO Remission	Endoscopic response: See SES-CD section above. PRO remission: See CDAI section above.	Composite of Endoscopic Response and PRO Remission	Proportion of subjects achieving both endoscopic response and PRO remission at Week x. Endpoints: 
 • Proportion of subjects achieving both endoscopic response and PRO remission at Week 12 • Proportion of subjects achieving both endoscopic and PRO remissions at Week 52

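### The below-150 route to CDAI response carries no baseline condition and entry sets no CDAI floor, so a subject whose CDAI worsens can be scored a responder.

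*SAP*

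**What the plan says.** **Entry.** Protocol 6.1, criterion [2], sets the symptom requirement: "as defined absolute SF ≥ 4 (loose and watery stools defined as Bristol Stool Scale Category 6 or 7) AND/OR AP ≥ 2 at baseline". Either symptom alone is therefore enough. Criterion [3] adds an endoscopic threshold ("have a SES-CD score ≥ 7 (centrally read" for ileal-colonic disease, at least 4 for isolated ileal disease). SES-CD is not a component of CDAI. No inclusion or exclusion criterion sets a CDAI minimum, although CDAI is scheduled at Visits 1 and 2.

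**CDAI categories.** Protocol 9.1.5 describes the index as "yielding a total score range of 0 to 600 points with a score of <150 points defined as remission". SAP Table AMAG.4.1 words the exploratory objective as "CDAI Response (defined as a decrease in CDAI of at least 100 points or CDAI <150", with no condition on the starting value. SAP Table AMAG.6.7 derives remission as "Proportion of subjects with CDAI Total Score <150 at Week x" and response as "Proportion of subjects achieving a CDAI reduction of ≥ 100 from baseline or CDAI <150 at Week x". Neither derivation refers to whether baseline was already below 150.

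**Analysis.** SAP Table AMAG.6.8 analyses both at Week 12 by logistic regression with non-responder imputation in the ITT population. Each dose is compared with placebo (Table AMAG.6.5). CDAI remission at Week 52 among Week 12 CDAI responders is descriptive, in EHO Group 2.

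**Neighbouring endpoints.** In Table AMAG.6.7, PRO remission, PRO response and PRO1 remission each require that SF and AP are no worse than at baseline.

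**The concern.** A response endpoint should record improvement. The 100-point limb does. The below-150 limb does so only if the subject started at or above 150, and entry does not ensure that. A subject below 150 at baseline already satisfies that limb before the first dose and keeps satisfying it through any worsening that stays under 150.

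Three things follow. The Week 12 response rate can include subjects who got worse. The Week 12 remission rate includes subjects who did not newly reach that state. Both groups can raise the rate in every arm and shrink the contrast with placebo. Finally, a subject wrongly counted as a responder enters the denominator of the Week 52 remission-in-responders summary, and may enter its numerator without ever having been at or above 150.

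**Working it through.** **Inputs.** CDAI weights from SAP Appendix 6, applied to 7-day totals: SF ×2, AP ×5, general well-being ×7. The further items are extra-intestinal manifestations ×20 each, antidiarrhoeal use ×30, abdominal mass ×10, haematocrit deficit ×6 and weight deviation ×1. Entry thresholds are from Protocol 6.1.

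**1. The plan's own power figure.** The documents give no power for the CDAI endpoints. The primary-endpoint figure (60 per arm, 35% vs 15%, two-sided alpha 0.10, Protocol 10.1) reproduces: a pooled chi-squared calculation gives 81.8% against the stated 81%. It is not affected by this point.

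**2. Can an eligible subject start below 150?** With all other items at zero:

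| Daily symptoms | Calculation | CDAI points |
|---|---|---|
| SF 4 | 4×7×2 | 56 |
| AP 2 | 2×7×5 | 70 |
| SF 4 and AP 2 | 56+70 | 126 |
| SF 4, well-being 1 | 56+1×7×7 | 105 |
| AP 2, well-being 1, haematocrit deficit 4 | 70+49+4×6 | 143 |

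All meet the symptom criterion and all are below 150.

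**3. Can such a subject worsen and still count?** SF 4/AP 0 to SF 6/AP 1 is 56 to 6×14 + 1×35 = 119. SF 0/AP 2 to SF 5/AP 2 is 70 to 5×14 + 2×35 = 140. Both changes are worsening, and both satisfy the below-150 limb. From 56, a whole-number score can rise by 93 points (to 149) and still be a response.

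**4. Do the other remission endpoints share the gap?** No. PRO2 at entry is at least 4×2 = 8 or 2×5 = 10, so PRO2 remission (below 8) cannot hold at entry. PRO remission needs SF at most 2.5 and AP at most 1, which contradicts the entry criterion. Endoscopic remission needs SES-CD below 4 (or below 2), against an entry minimum of 7 (or 4).

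**5. Size, by assumption only.** Let s be the share below 150 at baseline and k the proportion of them still below 150 at Week 12, equal in both arms. For rates p in the remaining subjects, the observed rate is p(1−s) + ks, and the difference is multiplied by (1−s). Take 15% (placebo) and 30% (LY) in the rest:

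| s | k | Placebo | LY | Difference (points) |
|---|---|---|---|---|
| 5% | 80-90% | 18.3-18.8% | 32.5-33.0% | 15×0.95 = 14.25 |
| 10% | 80-90% | 21.5-22.5% | 35.0-36.0% | 15×0.90 = 13.5 |
| 15% | 80-90% | 24.8-26.3% | 37.5-39.0% | 15×0.85 = 12.75 |

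**6. What a baseline restriction costs in power.** Same assumptions, 60 per arm, two-sided alpha 0.10, pooled chi-squared. At s = 10%, full-ITT power is 49-50%, against 59% in the 54 per arm with baseline at least 150. At s = 15%, it is 44-45%, against 57% in 51 per arm. Under these assumptions the smaller denominator costs less than the dilution.

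**The case against.** The strongest reply has four parts.

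- **Remission is a state.** The protocol itself defines a score under 150 as remission, and a subject at 145 is in that state whatever the starting value. This stands. A reader might infer that the CDAI remission definition is wrong, but the documents do not support that. What remains for remission is how its rate is read.
- **Change in CDAI is analysed elsewhere.** The SAP analyses change in CDAI total score by MMRM with baseline terms, plus ANCOVA with mBOCF, so a rise from 56 to 119 appears there as +63. This also stands, and it limits the damage. It does not correct the response rate.
- **The endpoints have low standing.** They are listed in the SAP as exploratory and not in the protocol, and the Week 52 conditional version has no treatment comparison. This stands, and it keeps the point minor.
- **Near-threshold examples are fragile.** A subject with SF 4, AP 1 and well-being 1 scores 140 only if every other item is zero; a haematocrit deficit of 3 adds 18 and gives 158. The mechanism survives because the lower combinations (56, 70) leave wide room, but how common such subjects are is unknown.

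A reader might also infer bias towards LY3074828. The documents do not support that: randomisation is expected to spread these subjects over the arms, so the expected effect is dilution. Chance imbalance is possible, most of all in the 200 mg and 600 mg arms (1/6 of 180, about 30 each). Nor are these subjects barred from a real response: one starting at 120 could still fall by 100 points. If more placebo than LY subjects rise above 150, the dilution is smaller than shown.

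**Conclusion.** The point holds for the below-150 limb of CDAI response. On the plan's wording, an eligible subject can start below 150, worsen, and be counted as a Week 12 responder, while three neighbouring PRO endpoints already guard against this. For CDAI remission the definition is sound, but the all-ITT rate mixes subjects who reached remission with subjects who began in it.

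The size cannot be established from the documents, because the share below 150 at baseline is not given. If it is 5-15%, with 80-90% staying below 150 equally in both arms, a 15-point difference shrinks by 0.75 to 2.25 points. The primary endpoint, its power and the MMRM on CDAI change are untouched. This is a minor correction that would be good to make.

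**What to change.** 1. In Table AMAG.6.7 (and the matching row of Table AMAG.4.1), add a no-worse-than-baseline condition to the below-150 limb of CDAI response. Keep the ITT population. This uses the guard the SAP already applies to the PRO endpoints. It also leaves the limb its purpose for subjects starting between 150 and 249, who cross 150 before they can fall by 100.
2. In Table AMAG.6.8, add an analysis of CDAI response, CDAI remission and CDAI remission in CDAI responders restricted to subjects with baseline CDAI of at least 150, alongside the planned analyses. For the Week 12 comparisons the subset is fixed before treatment, so the randomised comparison is preserved within it.
3. Report the number of subjects below 150 at baseline in each arm, so that the dilution can be judged from data.

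The cost is a sentence or two in the SAP and one subset flag, using baseline CDAI that is already collected. The downside is one more analysis, on a smaller denominator, for exploratory endpoints. The guard alone does not remove subjects who start below 150 and stay level or improve slightly, which is why the restricted analysis is also needed.
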